 Of which 300 confirmed DILI cases

Secondary endpoints

We will collate detailed and comprehensive data using an electronic case report form (eCRF) to achieve in-depth phenotyping. (A paper version for data collection is available as a separate document: Annex. 1 CRF.)

Levels of putative biomarkers in samples will be assessed and evaluated to determine correlation with diseases phenotype and likely value in diagnosis or prognosis.

Causality assessment: Causal relationships between the event and the drug will be assessed using the Roussel Uclaf Causality Assessment/Council of International Organization of Medical Sciences (RUCAM/CIOMS). DILI will be phenotyped and severity graded as recommended by the phenotyping standardization project [4].

Standard variables in DILI, such as type of liver damage, severity and chronicity, will be classified as recommended by the phenotyping standardisation project [4]. The type of liver damage will be defined as hepatocellular, cholestatic or mixed based on the ratio (R) between alanine transaminase (ALT) and alkaline phosphatase (ALP) expressed in times the upper limit of normal (ULN), R = (ALT/ULN) / (ALP/ULN). Hepatocellular damage is defined as R≥5, cholestatic damage ≤2 and mixed damage as 2<R<5. The R value will be calculated from the first available analytical values after DILI initiation.

Severity of DILI will be graded as follows:

Mild: Elevated ALT/ALP concentration reaching criteria for DILI but total bilirubin (TBL) concentration <2x ULN

Moderate: Elevated ALT/ALP concentration reaching criteria for DILI and TBL ≥2x ULN, or symptomatic hepatitis

Severe: Elevated ALT/ALP concentration reaching criteria for DILI, TBL ≥2x ULN and one of the following:

• international normalized ratio (INR) ≥1.5

Pro-Euro-DILI Registry Protocol Page 11 of 32

- ascites and/or encephalopathy, disease duration <26 weeks and absence of underlying cirrhosis
- other organ failure considered to be due to DILI

Fatal or transplantation: Death or liver transplantation due to DILI

Disease duration will be graded as follows:

• **Persistent DILI:** Evidence of continued liver injury >3 months for hepatocellular or mixed type of liver damage and >6 months for cholestatic liver damage

• Chronic DILI: Evidence of persistent liver injury at >1 year after the onset of DILI

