Causal DILI agents will be classified according to World Health Organisation (WHO) anatomical therapeutic chemical (ATC) classification system. Associated diseases will be classified according to the WHO tenth edition of the international classification of diseases, ICD-10.

STUDY POPULATION

Recruitment will be over a nine year period (up to April 2024).

-For suspected DILI patients : 3-7 visits, (each visit lasting for up to 30mins). Each patient will be in the study for up to 6 months duration.

Follow-up: Each patient will have a clinical follow up until the event resolves or 12 weeks after the first event whichever occurs later. We will also follow-up outcomes in clinical notes over a 10 year period after recruitment where consent is given.

Enrolment:

We expect to enrol each case at the earliest opportunity possible, following the suspected DILI event (or AIH event) (up to a maximum of 8 weeks from diagnosis) when research team anticipates that they will meet inclusion criteria below. Each patient will be followed from the identification of hepatotoxicity until normalization of the analytical liver profile.

Enrolment will begin once a patient has been clinically diagnosed with suspected DILI and gives consent to take part in the study. In all instances the visit schedule should be adapted to routine hospital procedures in order to facilitate patient participation as well as avoid additional hospital costs (see diagram below).

- Control participants (on medication or untreated but without DILI symptoms): A

single study visit of up to 30 minutes duration. Controls will be required to provide biological samples, demographic and medical data will also be collected.

Study Duration:

Enrolment will end at 9 years from the start of the study (Apr 2024) or once the recruitment target has been met, whichever is soonest.

INCLUSION CRITERIA

All patient and control groups:

- Aged 18 years and over
- Able to give written informed consent OR consent provided by consultee (personal or nominated) for potential participants with suspected DILI who lack capacity to give written informed consent.

A. Suspected DILI Patients:

Adults diagnosed with suspected acute DILI (within 8 weeks of diagnosis) and meeting the following criteria will be included:

1. Meets one of the following analytical thresholds at enrolment (visit 1)

- alanine transaminase (ALT) exceeding 5 times upper limit of normal (ULN) OR
- alkaline phosphatase exceeding 2 times ULN OR

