If the PI or Investigator and research team are unable to identify/appoint a suitable personal consultee then efforts will be made to nominate a health professional who is unconnected with the research project to act as a professional consultee. We will firstly ask a member of the standard medical care team of the person who lacks capacity if they would consider taking on the role. The professional consultee will be required to perform the same role as a personal consultee in advising the research team but they may not know the person who lacks capacity and therefore may be required when attempting to determine what the person's wishes and feelings about the research would be if they had capacity, seek the views of any family, friends/carers of the person who lacks consent, or seek other

professional colleagues with an interest in the person's welfare or condition. We will continue to assess capacity throughout the research and will seek consent as soon as feasible.

All consultees (personal and professional) will receive a copy of the consultee information sheet to read. If and when the participant regains capacity, consent will be sought from the participant retrospectively, and will be withdrawn from the study if consent is not given.

We currently have no sites or plans to recruit from sites in Northern Ireland. If this was to occur, we are aware that Northern Ireland follow different legislation and a different process would need to be followed regarding the documentation. We would ensure that this process was followed correctly. We are currently seeking approval to recruit these patients in England and Wales only. We plan to put a future application to a Scotland A REC in order to allow us to recruit patients who lack capacity in Scotland.

STUDY PROCEDURES

SAMPLE COLLECTION Suspected DILI patients

Biological samples will be collected from each enrolled patient on up to 7 occasions (see diagram below). These visits will take place as soon as possible following acute presentation; there will be a time lag of up to 8 weeks between identification of an episode of DILI by the team responsible for the clinical care of the patients and the patient giving consent to take part in the study. Patients' blood tests must meet the eligibility inclusion criteria on the day they are enrolled (Day 0, visit 1) in order to continue to participate in the study.

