As far as possible, research bloods will be collected at the same time as bloods for clinical care of the patient and visits arranged to coincide with hospital appointments. Preferred visit times are given below but visits outside the times will not be considered as a protocol deviation. Appendix 1 lists the standard clinical care analyses (including ultrasound, viral hepatitis screen, autoantibody screen, haematology and blood chemistry), and research assessments which may be carried out at each visit.

Patients with suspected DILI who are recruited and subsequently found to not have drugrelated injury will continue to provide further samples for this research (as detailed in the PIS). Visit 2 will be 7 ± 8 days from Visit 1. Visit 3 will be 30 ± 20 days after the Visit 1

For those who are in-patients (hospitalised at the time of acute DILI) we will secure additional data and samples on up to 2 further time points (termed visit 1B and Visit 1C) during the period of the patient's hospitalization. In such cases samples will be collected as part of clinical care and additional samples collected for research purposes. If patients continue to have DILI symptoms with raised liver enzymes (i.e. ALT, ALP or total bilirubin levels exceeding the normal range) at Visit 3, a further visit after approximately 3 months (Visit 4) will be arranged to collect the same set of samples. If enzymes remain above normal at this visit, samples will be collected again approximately 3 months later at Visit 5.

Sampling Schedule

- At each visit a delegated member of the research team will collect:
- Up to 80ml of blood. See most recent study presentation and/or sample collection SOP for details.
- Up to **50 ml of urine** (if possible)
- A Stool sample will also be collected (if possible).

Patients may be consented and samples collected at their home if appropriate and with permission of the PI. Nursing staff would be required to follow their Trust's lone working policy and code of practice.

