All routine laboratory analysis will be done by appropriate hospital as part as normal patient care. Blood will be processed for storage of serum and plasma as outlined in the SOP. Data and all appropriate documentation will be stored for a minimum of 25 years after the completion of the study, including the follow-up period.

We will collate detailed and comprehensive data using an electronic case report form (eCRF) to achieve in-depth phenotyping.

The procedure for data removal in the event of withdrawal of consent is described on pg 25.

Statistical Analyses

Researchers will be blinded to patient type/group being investigated – samples will be anonymized and labelled only with study ID code. Study groups will be compared using T-tests and non-parametric testing to identify biomarkers which distinguish DILI.

STUDY MANAGEMENT

The day-to-day management of the study will be co-ordinated through Nottingham Digestive Diseases Centre and NIHR Nottingham Biomedical Research Centre.

SPONSOR

Nottingham University Hospitals NHS Trust will act as the main sponsor for UK based sites for this study. Delegated responsibilities will be assigned to the NHS trusts taking part in this study.

FUNDING

Participant stipends and payments

Participants will not be paid to participate in the study. Travel expenses will be offered for any hospital visits in excess of usual care.

AUDITS

The study may be subject to inspection and audit by Nottingham University Hospitals under their remit as sponsor and other regulatory bodies to ensure adherence to GCP and the NHS Research Governance Framework for Health and Social Care (2nd edition).

STUDY CONDUCT

Study conduct will be subject to systems audit for inclusion of essential documents; permissions to conduct the study; CVs of study staff and training received; local document control procedures; consent procedures and recruitment logs; adherence to procedures defined in the protocol (e.g. inclusion / exclusion criteria, timeliness of visits); accountability of study materials and equipment calibration logs.

STUDY DATA

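### The only tests named for the biomarker comparisons have no patient or time term, so they cannot properly use the serial, outcome-dependent samples the protocol collects

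*Protocol*

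**What the plan says.** Protocol, Statistical Analyses, names the method: "Study groups will be compared using T-tests and non-parametric testing to identify biomarkers which distinguish DILI". It gives no unit of analysis, no visit and no method for repeated measurements.

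The sampling scheme is serial:

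- Study Population: "For suspected DILI patients : 3-7 visits, (each visit lasting for up to 30mins". Sample Collection: "Biological samples will be collected from each enrolled patient on up to 7 occasions".
- Inpatients have Visits 1B and 1C as well: "we will secure additional data and samples on up to 2 further time points".
- Visit 4 is held only if liver values are still raised at Visit 3. Then: "If enzymes remain above normal at this visit, samples will be collected again approximately 3 months later at Visit 5". The footnotes to Appendix 1 repeat these conditions.
- Patients enrolled as suspected DILI and later found to have another cause become symptomatic controls and stay on the same schedule (Healthy Control Group section). The Exclusion Criteria section makes them a separate study group for analysis.
- Other controls have one visit: "A single study visit of up to 30 minutes duration".
- Enrolment, and so Visit 1, may be up to 8 weeks after diagnosis (Enrolment; Sample Collection).

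The secondary endpoint reads: "Levels of putative biomarkers in samples will be assessed and evaluated to determine correlation with diseases phenotype and likely value in diagnosis or prognosis". The Study Summary objectives ask for samples at onset and at follow-up. Proposal Aims puts forward a hypothesis about the transition from an adaptive response to serious DILI. The primary endpoint is the acquisition of samples and data.

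**The concern.** A two-sample t-test or rank test assumes independent observations. It cannot recognise that several samples come from one patient, nor when in the illness they were taken. The protocol pairs these tests with a design in which the two groups of most diagnostic interest are sampled repeatedly, and in which sicker or slower-resolving patients contribute more samples.

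Each way of applying the sentence has a cost:

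1. **All samples pooled.** Standard errors are too small, and group means lean towards hospitalised and persistent cases.
2. **A separate test at each visit.** The correlation problem goes away, but Visits 4 and 5 then compare only patients who have not resolved.
3. **Visit 1 only.** The error rate is right, but the follow-up samples play no part, although the hypothesis concerns change within a patient. Visit 1 also falls at varying times after onset, and the tests cannot adjust for that.

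At stake is which markers are carried forward as distinguishing DILI. Samples and data go to several collaborating groups, who could each read the sentence differently.

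**Working it through.** The protocol gives no alpha, power or sample-size calculation (the Study Summary lists the sample size estimate as not applicable), so there is no stated figure to reproduce.

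**Inputs from the protocol**
- Visits per suspected case: 3 (Visits 1, 2, 3) to 7 (adding 1B, 1C, 4, 5).
- 430 suspected and 300 confirmed cases, so 430 − 300 = 130 symptomatic non-DILI if every unconfirmed case joins that group.
- One visit for other controls.

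**Assumptions, not in the protocol**
- Two-sided alpha of 5%.
- Within-patient correlation ρ of a marker from 0.2 to 0.8.
- Number of single-visit controls 100 to 300.
- Pooling of all samples as if independent. This is tested as a scenario only.

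**Step 1. DILI versus symptomatic non-DILI, both sampled m times**

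Design effect DE = 1 + (m − 1)ρ. Actual error = 2 × [1 − Φ(1.96/√DE)].

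| m | ρ = 0.2 | ρ = 0.5 | ρ = 0.8 |
|---|---|---|---|
| 3 | DE 1.4, 9.8% | DE 2.0, 16.6% | DE 2.6, 22.4% |
| 5 | DE 1.8, 14.4% | DE 3.0, 25.8% | DE 4.2, 33.9% |
| 7 | DE 2.2, 18.6% | DE 4.0, 32.7% | DE 5.8, 41.6% |

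Example: m = 3, ρ = 0.5 gives 1.96/√2 = 1.386 and an error of 16.6%, or 16.6/5 = 3.3 times nominal. The extremes are 9.8/5 = 2.0 and 41.6/5 = 8.3 times.

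A simulation of 300 versus 130 patients with no true difference and a mixed number of visits (50% with 3, 20% with 4, 20% with 5, 10% with 7; mix assumed) gave 12.7% to 30.2% for the t-test and 11.6% to 32.8% for Mann-Whitney over the same ρ. Rank tests do not avoid the problem.

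**Step 2. One value per patient**

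m = 1 gives DE = 1 and 5.0%. The simulated error using Visit 1 alone was 4.8% to 6.5%, which is nominal apart from simulation noise.

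**Step 3. DILI, pooled, versus n single-visit controls**

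The variance is understated by the factor V = (DE/N + 1/n)/(1/N + 1/n), where N is the number of DILI samples. Take an assumed mix of 3, 4, 5, 6 and 7 visits in 40, 20, 20, 10 and 10% of patients. The mean is 4.3 and the mean square 20.3, so N = 300 × 4.3 = 1,290 and DE = 1 + (20.3/4.3 − 1)ρ.

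- ρ = 0.2, n = 100: DE = 1.74, V = 1.05, error 5.6%.
- ρ = 0.8, n = 300: DE = 3.98, V = 1.56, error 11.7%.

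Simulation over the same range gave 5.7% to 11.3%. This is about 1.1 to just over 2 times nominal.

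**Step 4. Weighting if pooled**

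A 7-visit patient counts 7/3 = 2.3 times a 3-visit patient, and a 5-visit patient 5/3 = 1.7 times. If 20% of patients gave 7 samples and the rest 3, that 20% would supply 0.2 × 7/(0.2 × 7 + 0.8 × 3) = 1.4/3.8 = 37% of the data.

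**The case against.** The strongest reply is that nothing in the protocol says serial samples will enter a test as separate observations. It compares study groups, and the Study Summary objective speaks of levels in patients and control groups, which reads naturally as one value per person. Referring to marker levels in samples says where a marker is measured, not what the unit of analysis is. Choice of visit and any repeated-measures model could sit in a statistical analysis plan that is not shown. **This stands.** A reader might infer that the planned analysis has an inflated error rate, for instance 3 to 6 times nominal. The documents do not support that: pooling is not stated, and that multiple holds only near a correlation of 0.5, which the protocol does not give.

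Other limits also stand:

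- The upper end of the range has every patient giving 7 samples. Everyone would have to be hospitalised and still abnormal at both Visit 3 and Visit 4, which is not a realistic average.
- Patients below the laboratory thresholds at Visit 1 are not to be invited back. Any counted among the 430 would give one sample, so 130 serially sampled symptomatic controls is an upper figure.
- Comparing non-resolvers at Visits 4 and 5 is a legitimate question if it is described as such.

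The reply does not remove the mismatch. The protocol goes beyond leaving the method open: it names one, and that method has no place for repeated samples or time since onset, although follow-up sampling and a hypothesis about transition are central to the study.

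**Conclusion.** The point holds as a mismatch between the named method and the design, with a conditional risk attached. T-tests and rank tests are sound with one value per patient, but they cannot make proper use of the follow-up samples.

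If serial samples were pooled as independent, the false-positive rate would be roughly 2 to 8 times nominal for DILI versus symptomatic non-DILI. This assumes a within-patient correlation of 0.2 to 0.8 and 3 to 7 visits in both groups. Against single-visit controls it would be about 1.1 to just over 2 times nominal, for an assumed 100 to 300 controls. Hospitalised and persistent patients would be over-weighted. These are sizes of a risk, not error rates of the plan as written.

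A reader might also infer that the study's main result is threatened. It is not: the primary endpoint is acquisition of samples and data, and only the secondary biomarker comparisons are affected. The change should be made, but the study does not depend on it.

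**What to change.** Replace the sentence in Statistical Analyses with two rules:

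1. T-tests or rank tests between groups use one value per participant: the Visit 1 sample for DILI cases and symptomatic controls, and the single visit for other controls.
2. Serial samples from the DILI and symptomatic non-DILI groups are analysed with a linear mixed model on the marker (log scale where appropriate), with a participant random effect and fixed effects for group, time since onset and group-by-time. Visits 1B, 1C, 4 and 5 enter only through this model, never as extra observations in a t-test or rank test.

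The model removes the false independence and takes account of the varying delay to Visit 1. It does not by itself remove all selection at Visits 4 and 5, because those visits are triggered by liver values rather than by the marker. Late-visit estimates should be read with that in mind.

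The cost is a few lines of text and slightly more analysis work. No new patients, samples or visits are needed.

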Objectives	 To set-up an international European electronic registry of patients with idiosyncratic DILI, (iDILI) enrolled prospectively with the collation of indepth phenotyping: including details of drug dose, duration, concomitant medications, host demography, comorbidity including insulin sensitivity as well as the course of the event. To collect and store biological samples (blood, urine, stool and liver biopsy) from patients with suspected idiosyncratic DILI and the symptomatic non-DILI control group through the course (at onset and follow-up) of the event. To collect and store biological samples (blood, urine and stool) from control patients at a single visit. To make biosamples available for collaborative research through a dedicated biobank. To determine and analyse individual phenotypes and biochemical and cellular component levels in patients and control groups in order to develop translatable disease biomarkers
Study Configuration	Case controlled multi-centre study for the collection, analysis and storage of biological samples and data (medical, demographic and clinical).
Setting	Secondary care (hospital based)
Sample size estimate	N/A
Number of participants	 UK cohort: 150 suspected DILI cases (symptomatic) 20 cases of autoimmune hepatitis with DILI-like symptoms* Total, including European cohort: 300 confirmed DILI cases (50 in the UK)
	diagnosis).

Description of interventions	DILI patients, symptomatic non-DILI patients: Blood, urine and stool samples will be collected at each visit.
	We plan to additionally collect any available surplus liver biopsy or blood samples taken as part of clinical care (and any archived paraffin sections taken previously as part of clinical care).
Duration of study	Recruitment will be over a 9 year period (to Apr 2024)

INTRODUCTION

Background

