This is a European multicentre collaboration consisting of members of the Pro-Euro-DILI COST Consortium. This is coordinated by 2 centres: The University of Nottingham Nottingham Digestive Diseases Centre (NDDC) within the NIHR Nottingham BRC in the UK. and The Malaga Scientific Research Institute, Spain. Both coordinating centres will be responsible for the adjudication of each potential DILI case entered into the Pro-Euro-DILI Registry database. Both will share responsibility for the overall data monitoring, causality assessment of cases and the organisation/scheduling of regular conference call meetings and annual meetings.

Participating European Centres: (Incl both coordinating centres)

Each Centre will obtain ethical approval for the study, nationally and locally and form links with their local regional liver transplant unit. Each centre will be responsible for the collection of biological samples and the shipment of samples for analysis or storage at Nottingham BRC or Charite, or to an approved research tissue bank for long term storage (when the study ends). Samples will be stored at -80°C and shipped in batches.

Each Centre will also be responsible for entering the corresponding data into the Pro-Euro DILI Registry database (developed by Coresoft Clinic S.L, http://www.coresoft.es), available online. Tutorials on data entry and database implementations will be organized by the co-ordinating centres (Málaga and Nottingham) if required.

The web-based application and data will be hosted at Malaga University servers, with automated data backups on a daily basis, a report system for successful backup monitoring and reliable network connectivity. The software strictly follows the regulations imposed by the European Union ensuring that registries are secure and protected by the law. Furthermore, the software follows the Declaration of Helsinki requirements to ensure protection of patient's rights. No data that can reveal the patients identity will be entered into the database. Internet access to the registry platform is password protected and all stored passwords will be encrypted. Subsequent transfer of datasets for analysis will follow agreed data transfer procedure and adhere to data protection standards.

Collaborating centres include (but will not be limited to):

Primary endpoint

Acquisition of clinical samples and clinical data collected from a total of (across all sites in Europe):

430 suspected DILI cases (symptomatic)

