Healthy Control Group:

Adults who are exposed to the same drugs (as those responsible for DILI) without developing DILI will be identified. The Chief Investigator will access hospital pharmacy databases to identify patients taking specific drugs of interest. Then patients exposed to particular drugs without developing DILI will be invited to participate in the study as a control group. In the UK this will be done at the Nottingham site initially, extending to other sites where appropriate.

We will also advertise through BRC website (https://nddcbru.org.uk/pro-euro-dili) (appendix 2 shows screen shot) and social media pages (Facebook and Twitter) to invite people who have taken the particular drugs to contact us if they are interested in participating in the study (as control group).

A proportion of patients who are suspected to have DILI and enrolled as cases will be found to have an alternative explanation for their clinical manifestation found on subsequent investigation. The data and samples taken from these patients will be retained in the study and termed 'symptomatic controls' for analysis purposes. Sample and data collection will be continued in line with confirmed DILI participants.

INFORMED CONSENT

The process for obtaining participant informed consent will be in accordance with the REC guidance, and Good Clinical Practice (GCP) and any other regulatory requirements that might be introduced. Since DILI symptoms are acute and patients often present in emergency departments with sudden onset of severe symptoms, a long period (e.g. 24h) to consider consent is often difficult to provide in order to recruit patients while symptomatic and without asking patients to make additional hospital visits. Therefore, where appropriate, patients will be given a reasonable time period (ideally1 hour without disturbance), to read the patient information sheet and consider enrolment before being approached for consent by the research team. Appropriate steps will be taken to ensure that the patient is able to discuss participation in the study with those not involved in the research. The investigator or

Pro-Euro-DILI Registry Protocol Page 15 of 32

their nominee and the participant or other legally authorised representative shall both sign and date the Consent Form before the person can participate in the study.

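### The named t-tests and rank tests take no account of country, although the recruitment targets imply that DILI cases come mostly from outside the UK and symptomatic non-DILI controls mostly from within it

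*Protocol*

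**What the plan says.** The analysis is fixed in one sentence under Statistics and Data Analysis, Statistical Analyses: "Study groups will be compared using T-tests and non-parametric testing to identify biomarkers which distinguish DILI". The same paragraph blinds researchers to patient group. No section mentions stratification, matching or adjustment by country or centre.

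The group sizes come from two places:

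- **Primary endpoint:** "Acquisition of clinical samples and clinical data collected from a total of (across all sites in Europe" introduces the totals "430 suspected DILI cases (symptomatic" and "Of which 300 confirmed DILI cases". The UK is therefore inside these totals.
- **Study Summary, Number of participants:** for the UK, "150 suspected DILI cases (symptomatic" and "20 cases of autoimmune hepatitis with DILI-like symptoms". For the whole study, "300 confirmed DILI cases (50 in the UK".

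Under Exclusion Criteria, suspected cases later found to have another cause stay in the study and are analysed as a separate group. Identifying Participants calls them symptomatic controls. DILI versus symptomatic non-DILI is therefore a planned comparison.

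Sample Collection has each centre process its own samples under common operating procedures. Study Plan and Coordinating Centres add frozen storage, batch shipment and analysis at more than one possible laboratory.

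**The concern.** A two-sample t-test or an ordinary rank test compares all DILI patients with all controls, wherever they were recruited. If one group is mainly from the UK and the other mainly from elsewhere, a marker that differs between UK and non-UK samples for any reason other than DILI will also differ between the groups. Such reasons could include local processing, storage and shipment, time from injury to sampling, or case mix. Enrolment may come up to 8 weeks after diagnosis, and visits outside the preferred times are not deviations, so sampling time can vary between centres.

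At stake is the biomarker secondary endpoint. A marker of where a sample was taken could be reported as a marker of DILI, and a real marker could be masked if the regional difference ran the other way.

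**Working it through.** **Inputs.** Europe: 430 suspected, 300 confirmed (Primary endpoint). UK: 150 suspected, 50 confirmed (Study Summary). The protocol gives no table by country, power calculation or marker SD, so it has no figure of its own to reproduce.

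**Step 1: implied table.** Assume that every unconfirmed case becomes a symptomatic control.

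| | DILI | Symptomatic non-DILI |
|---|---|---|
| UK | 50 | 150 − 50 = 100 |
| Non-UK | 300 − 50 = 250 | 130 − 100 = 30 |
| Total | 300 | 430 − 300 = 130 |

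Non-UK share: 250/300 = 83.3% of DILI and 30/130 = 23.1% of controls, a difference of 0.603. Odds ratio between group and region: (250/50)/(30/100) = 16.7. Counting the 20 UK autoimmune hepatitis cases as extra controls gives 30/150 = 20%.

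**Step 2: effect of losses.** If x of the 100 unconfirmed UK cases do not become controls and the 30 non-UK controls all remain, the non-UK control share is 30/(130 − x).

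- x = 20: 30/110 = 27%
- x = 50: 30/80 = 37.5%
- x = 80: 30/50 = 60%

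To match 83.3%, total controls would have to be 30/0.833 = 36, leaving only 6 in the UK. Losses outside the UK would push the share down again.

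**Step 3: false-positive rate.** Assume no DILI effect, a within-region SD of 1 and a regional shift of d SD. The spurious group difference is 0.603 × d. Its standard error is √(v₁/300 + v₀/130), where v = 1 + d²p(1 − p) and p is the group's non-UK share. With t = difference/SE, the two-sided 5% rejection rate is 1 − Φ(1.96 − t) + Φ(−1.96 − t).

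| d (assumed) | Spurious difference | SE | t | Rejection rate |
|---|---|---|---|---|
| 0.10 | 0.060 | 0.105 | 0.57 | 9% |
| 0.25 | 0.151 | 0.106 | 1.43 | 30% |
| 0.50 | 0.301 | 0.107 | 2.81 | 80% |

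These rates depend on Step 1. In the extreme case of Step 2 (x = 80: share difference 0.833 − 0.600 = 0.233, 50 controls), the same formula gives about 5%, 7% and 12%. With x = 50 (difference 0.458, 80 controls) it gives about 6%, 15% and 43%.

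**Step 4: price of stratifying (UK versus non-UK, full targets).**

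- Pooled: SE = √(1/300 + 1/130) = 0.105.
- Stratified: information = 50×100/150 + 250×30/280 = 33.3 + 26.8 = 60.1, so SE = 1/√60.1 = 0.129.
- Variance ratio: (0.129/0.105)² = 1.51.
- Difference detectable with 80% power (two-sided 5% assumed): 2.80 × 0.105 = 0.29 SD pooled and 2.80 × 0.129 = 0.36 SD stratified.

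**The case against.** The best reply is that one sentence naming families of tests does not forbid adjustment, and that covariates are often left to an analysis plan. A van Elteren test is itself non-parametric. This has some force: the sentence does not call the tests unadjusted. It does, however, name t-tests, which take no stratum or covariate, and a team following it literally would ignore region.

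The table also deserves caution. It comes from subtracting recruitment targets. Patients below the visit 1 thresholds are not invited back, and only those found to have another explanation become symptomatic controls, so the 23% and the odds ratio of 16.7 depend on one assumption. The implied confirmation rates, 50/150 = 33% in the UK and 250/280 = 89% elsewhere, may mean that the targets were set on different bases. The imbalance shrinks with losses but persists in every loss scenario above.

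Several stronger readings are tempting but unsupported:

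- **Every centre effect becomes a false DILI marker.** Only effects aligned with group bias the comparison.
- **Drugs and populations are known to differ by country.** The protocol does not say so, and it gives no size for d.
- **Drug-exposed controls are equally unbalanced.** Their number and country mix are not in the legible text. The sentence "In the UK this will be done at the Nottingham site initially, extending to other sites where appropriate" says nothing about controls elsewhere.
- **The study's main aim fails.** The primary endpoint does not depend on this analysis.

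Blinding and common procedures limit measurement and handling differences. They do not break the link between group and region.

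**Conclusion.** The concern holds for DILI versus symptomatic non-DILI. On the recruitment targets the two groups differ sharply in region (about 83% versus 23% non-UK), and the tests named in the protocol ignore region.

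The imbalance makes confounding possible; bias arises only if marker levels differ by region for reasons unrelated to DILI. At the full targets, the error rates of about 9%, 30% and 80% show what shifts of 0.10, 0.25 and 0.50 SD would do. They are illustrations, not estimates, and fall if many unconfirmed UK cases are lost.

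This is a worthwhile correction to the biomarker analysis, not a fault that undermines the registry. It can be made without changing recruitment.

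**What to change.** Replace the analysis sentence so that DILI is compared with symptomatic non-DILI within region:

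- Stratify by or adjust for country, at least UK versus non-UK, and for centre where both groups are present. Use regression with a country term, or the van Elteren test as the rank version.
- Adjust for age and sex.
- Show UK and non-UK estimates beside the pooled one.
- Assay cases and controls from the same country on the same plates. This must be settled before assay because it cannot be repaired afterwards.
- Adjust for time from onset to sample only in comparisons among symptomatic patients, and only if onset date is recorded. Appendix 1 does not list it, and drug-exposed controls have no onset.

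The cost is wording, plate layout and precision. The SE rises from 0.105 to at least 0.129 SD, and the detectable difference from 0.29 to at least 0.36 SD. Finer strata cost more: about 30 non-UK controls spread over several countries will leave some strata with no controls, and those contribute nothing.
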